8.2.2 Control Intervention

Participants in the control arm will receive SOC treatment according to local guidelines.

8.3 Dose / Device modifications

The only modification will be omission of subsequent doses of conestat alfa if the participant develops a type 1 allergic reaction including an anaphylactic reaction after any dose of conestat alfa. Other dose modifications are not expected, in particular will conestat alfa not be ceased if the patient deteriorates already during the conestat alfa treatment interval. If the patient is discharged or transferred to another facility the intervention will be ceased.

8.4 Compliance with study intervention

Conestat alfa syringes for all administration time points on a given day will be prepared by a regular ward nurse. The study drug including the exact time for administration of the first and subsequent syringes will be entered into the electronic prescribing system/chart or added to the paper chart. As this study involves IV administration of the IMP by nurses, patient compliance measures are not necessary. IMP will be administered by a nurse according to the site's standard procedures. Two nurses will check the IMP with respect to dose, study number and patient's identity before administration to the patient. Nurses will document the syringe number and the time of administration in the electronic or paper chart.

8.5 Data Collection and Follow-up for withdrawn participants

Patients can leave the study at any time for any reason if they wish to do so without any consequences. The Investigator can decide to withdraw a patient from the study for medical reasons. A patient who experiences a treatment-emergent anaphylactic reaction will not be permitted to receive further treatment with conestat alfa.

Patients who withdraw informed consent will not be followed up. Although incomplete, data and samples collected up to the discontinuation will be analyzed. Personal data, samples and the confidentiality of these patients will be managed according to the same standards as per other evaluated completed patients.

Patients who are withdrawn from the study because they did not receive any study medication will not be followed up.

Patients who are discontinued from the study because of a type I allergic reaction during the treatment phase are followed in the same fashion as planned for all participants.

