5. STUDY OUTCOMES

5.1 Primary Outcome

The primary endpoint will be the disease severity on the 7-point Ordinal WHO scale on day 7 (for the current study, score 0 will be omitted and score 6 and 7 will be combined). This endpoint has been suggested by WHO for clinical trials in patients with COVID-19. The ordinal scale measures illness severity over time.

Patient State	Descriptor	Score
Uninfected	No clinical or virological evidence of infection	0
Ambulatory	No limitation of activities	1
	Limitation of activities	2
Hospitalized Mild disease	Hospitalized, no oxygen therapy	3
	Oxygen by mask or nasal prongs	4
Hospitalized Severe Disease	Non-invasive ventilation or high-flow oxygen	5
	Intubation and mechanical ventilation	6
	Ventilation + additional organ support – pressors, RRT, ECMO	7
Dead	Death	8

Figure 3: WHO ordinal scale for clinical improvement. For the current study, score 0 will be omitted, and score 6 and 7 will be combined.

Patient State	Description	Score
Outpatient	No limitation in activities	1
	Limitation in activities	2
Hospitalized Mild disease	No oxygen therapy	3
	Oxygen by mask or nasal prongs	4
Hospitalized Severe disease	Non-invasive ventilation or high-flow oxygen	5
	Intubation, mechanical ventilation +/- additional organ support	6
Death	Death	7

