7.4 Criteria for withdrawal / discontinuation of participants

Subjects may voluntarily withdraw from study participation at any time without having to provide a reason. Subjects may be withdrawn because of the appearance of a new health condition requiring care or medications prohibited by the protocol, unacceptable adverse event, refusal to continue treatment, or at the Investigator's discretion if it is in the subject's best interest.

A subject who withdraws informed consent before randomization or who develops a violation of the selection criteria before randomization is defined as a screening failure. No follow-up of screening failures will be performed.

Participants who withdraw informed consent, who do not fulfil inclusion/exclusion criteria after obtaining informed consent AND have not received any study medication will be withdrawn from the study.

Participants who experience a type I allergic reaction after any dose of study medication will be discontinued from further study interventions. Withdrawn or discontinued participants will not be replaced. Follow-up for all patient groups will be explained in Section 9.2.5.

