9.2.5 Assessments in participants who prematurely stop the study

Patients who are withdrawn from the study will remain in the trial for the purpose of follow-up and data analysis and will be followed as planned with the following exceptions.

- Patients, who withdraw consent for all study measures, will be asked to have assessments performed as appropriate for the final 4 week study visit (i.e. a structured telephone interview). The same approach applies for all active study participants if the trial is stopped early. Patients who withdraw consent are at liberty to refuse any or all individual components of the final assessment.
- Patients who are withdrawn because they have not received any study medication will not be followed up and will not receive a final study assessment.

Patients who discontinue the study because of safety concerns will be followed as planned. Patient with a type I allergic reaction will be referred to our Allergy department for further work-up.

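### Protocol 8.5 and 9.2.5 give conflicting follow-up rules for patients who withdraw consent, and neither asks for the day-7 score, so early full withdrawers enter the primary analysis with a carried-forward value

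*Protocol*

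**What the plan says.** Three sections of the protocol deal with patients who leave early.

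- **7.4** lists the grounds for withdrawal and then defers: "Follow-up for all patient groups will be explained in Section 9.2.5".
- **8.5** states "Patients who withdraw informed consent will not be followed up". It adds: "Although incomplete, data and samples collected up to the discontinuation will be analyzed". It says that patients discontinued for a type I allergic reaction are followed like everyone else. It has no separate rule for a patient who declines only further study drug or samples.
- **9.2.5** begins from the opposite default: "Patients who are withdrawn from the study will remain in the trial for the purpose of follow-up and data analysis", with follow-up as planned apart from listed exceptions. The exception that matters here reads: "Patients, who withdraw consent for all study measures, will be asked to have assessments performed as appropriate for the final 4 week study visit". It also protects refusal: "Patients who withdraw consent are at liberty to refuse any or all individual components of the final assessment".

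On the endpoint, 5.1 states: "The primary endpoint will be the disease severity on the 7-point Ordinal WHO scale on day 7". The three secondary endpoints in 5.2 run to day 14. Section 9.3.1 (Visit 5) already plans a short telephone call to score patients discharged before day 7. Visit 7 records the scale at week 4. Under 11.4.1 the primary analysis covers all randomised patients, and 11.4.1 and 11.5 fill missing primary values by LOCF. Section 6.2.2 says that participants and staff are not blinded.

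**The concern.** A site that opens 8.5, the section named for data collection after withdrawal, makes no further contact with a patient who withdraws consent. A site that follows 7.4 to 9.2.5 asks the same patient for a week-4 interview. The amount of week-4 safety and mortality data could then depend on which section a centre reads.

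The second part concerns the primary endpoint. Under either section, a patient who withdraws from all measures on day 2, say, is not asked for the day-7 score. LOCF then supplies an early inpatient score. Because patients know their arm, the decision to withdraw can depend on allocation, and so can the replacement of observed scores by carried ones. No later analysis can recover a score that was never collected.

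**Working it through.** **1. The two rules side by side**

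| Patient | 8.5 | 9.2.5 | Day-7 score requested? |
|---|---|---|---|
| Stops study drug or samples only | Not distinguished | Followed as planned | Yes under 9.2.5; unclear under 8.5 |
| Withdraws consent for all study measures before day 7 | No follow-up | Asked for week-4 assessment | No under either |
| Withdraws consent for all study measures after day 7 | No follow-up | Asked for week-4 assessment | Already recorded |

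The contradiction lies in the last two rows. The gap in the primary endpoint lies in the middle row only.

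**2. Inputs for an illustration**

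From 11.2: SD 1.5, relevant effect 1 point, 80 + 40 patients, looks at 40, 80 and 120 patients at a two-sided level of 0.0221. The planning figures can be reproduced. A two-sided t-test at 80% power needs 36.3 per arm, and dividing by the rank-test efficiency of 0.955 gives 38.0, the protocol's 38 per arm. Three looks at 0.0221 give an overall two-sided error of 0.0499 by simulation.

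The protocol states no withdrawal rate. What follows therefore uses assumed rates.

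**3. Shift in the treatment difference**

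Let p be the share of an arm that withdraws from all measures before day 7, and g the mean of carried score minus true day-7 score among them. Then

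shift (control minus treated) = p_control × g_control − p_treated × g_treated.

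- Controls only, p = 5% (2 of 40), g = 1 to 2: 0.05 to 0.10 points.
- Controls only, p = 10% (4 of 40), g = 1 to 2: 0.10 to 0.20 points.

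Against the 1-point effect this is 5% to 20%.

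**4. Effect on the test if there is no true difference**

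Each stage has about 13.3 controls and 26.7 treated, so the stage drift is shift / (1.5 × √(1/13.3 + 1/26.7)) = shift / 0.503. Simulating the three-look design gives:

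| Shift | Two-sided type I error |
|---|---|
| 0 | 5.0% |
| 0.05 | 5.3% |
| 0.10 | 6.0% |
| 0.20 | 9.3% |

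**5. How far this depends on the assumptions**

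- *Some withdrawers deteriorate.* Section 3.8 expects about 15-20% of hospitalised patients to progress to mechanical ventilation. Take withdrawers at score 4, with 80% truly at 2 and 20% truly at 6 on day 7: g = 0.8 × 2 − 0.2 × 2 = 1.2. With 5-10% withdrawal the shift is 0.06 to 0.12.
- *Withdrawal at score 3.* If a share q ends at 6 and the rest at 2, g = (1 − q) × 1 − q × 3 = 1 − 4q. This is zero at q = 25% and negative above it.
- *Withdrawal in the treated arm.* Equal p and g in both arms cancel. Treated-only withdrawal at the rates in step 3 gives −0.05 to −0.20.

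**6. Power**

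If lost scores carried no information at all, power at a true 1-point effect would be about 88% with no loss, 86% at 5% loss and 84% at 10% loss. Possible bias is therefore the issue more than power.

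**The case against.** The strongest reply is that 9.2.5 largely handles this already. It keeps withdrawn patients under planned follow-up, its exception is limited to those who withdraw consent for all study measures, and 7.4 names 9.2.5 as the governing section. That stands for patients who only stop drug or samples, and it narrows the point. It does not settle the conflict, because nothing in 8.5 says that it yields to 9.2.5.

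A second reply is that the week-4 contact is broader than it looks. Section 9.3.1 (Visit 7) covers ICU admission and mechanical ventilation and allows chart review, discharge summaries and contact with the general practitioner. A patient who agrees might thus supply earlier status retrospectively. This is fair for ventilation and vital status under 9.2.5. The day-7 score is still not requested, and 8.5 rules the contact out.

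A reader might infer three stronger claims that the protocol does not support:

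- *That the primary endpoint is lost for anyone who withdraws.* The patient stays in the all-randomised set with an LOCF value, and only full withdrawal before day 7 replaces the observed score.
- *That the bias favours conestat alfa.* This needs withdrawal concentrated among controls who then improve. The treated arm has nine injections and, in Basel, extra blood draws of its own, so treated patients also have reasons to withdraw.
- *That the day-7 score can simply be read from the chart.* This presumes permission to use the chart after consent is withdrawn. The consent pages are not in the text reviewed, so existing provisions cannot be judged.

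**Conclusion.** The point holds in a limited form. Sections 8.5 and 9.2.5 contradict each other for patients who withdraw consent, and this rests on the text alone. Neither section asks for the day-7 score, so a patient who withdraws from all measures before day 7 enters the primary analysis with a carried value.

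The size and direction of any resulting bias are unknown because no withdrawal rate is given. The 0.05-0.2 point range, and the type I error of 5.3% to 9.3% that goes with it, are illustrations. They depend on early withdrawal of 5-10% confined to controls and carried scores 1-2 points too high. Other plausible patterns shrink, cancel or reverse the shift. The case for a change is that a missing score which could depend on arm, in an open-label trial, can be partly avoided at very little cost. It should be corrected, but it does not by itself undermine the primary analysis.

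**What to change.** Replace the 8.5 sentence on consent withdrawal with one rule, worded identically to or cross-referring to 9.2.5:

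1. Patients who stop study drug, blood or urine sampling only are followed as planned, including the day-7 score.
2. Patients who withdraw consent are asked, with the right to refuse any part, for permission to record the day-7 WHO score, the day-14 ventilation status and the 28-day vital status. The day-7 score can come from the chart or from the short telephone call already planned for discharged patients.
3. If the patient refuses, nothing further is collected.
4. The patient's answer is recorded on the eCRF dropout form described in 12.2.

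The cost is one extra question to the withdrawing patient, a field on an existing form, and a wording change in the protocol and, if needed, the consent form. The rule cannot remove missing scores from patients who refuse, but it limits LOCF to those cases and makes practice the same across sites.

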11.4 Planned Analyses

11.4.1 Datasets to be analysed, analysis populations

A review of the database will be conducted in a blinded manner shortly before the database will be locked, and any decisions made at that meeting (blinded Data Review Meeting) concerning the statistical analysis, e.g., additional outcomes and populations, pooling of sites for efficacy analysis, will be documented in the Statistical Analysis Plan (SAP).

Missing data for the primary endpoint will be imputed by means of the Last-observation-carried-forward (LOCF) method.

Safety Population: The Safety Population is defined as all patients who received at least one dose of conestat alfa. Statistical analyses will be based on the actual treatment the patient received.

Full Analysis Set/Intent-to-Treat Population: The FAS/ITT Population is defined as all patients who are randomly allocated to a study arm. Statistical analyses will be based on the treatment arm to which the patient was allocated.

For quantitative data, the number of patients with non-missing information, means, medians, standard

deviations and extremes will be determined. For qualitative data, absolute and relative frequencies will be calculated. Moreover, changes from baseline (V2, d0) will be calculated.

Per Protocol Population: The PP Population is defined as all patients in the FAS/ITT Population who complete the study and who do not have any major protocol violations, including the following:

- Patients who had major inclusion/exclusion criteria violations.

Sufficient compliance is expected because of IV administration of the IMP.

The PP Population will be determined by a blinded review in the Data Review Meeting (DRM) of the data prior to database lock.

The primary efficacy analysis will be based on the FAS/ITT Population in this superiority trial; an additional efficacy analysis will be performed on the PP Population. The Safety Population will be used for all safety analyses.

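### Some randomised patients who received no study medication are not followed up, yet they stay in the ITT set with imputed outcomes, and the rule works differently in the two arms

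*Protocol*

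**What the plan says.** Three sections of the Protocol govern follow-up after withdrawal.

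- **7.4** first deals with patients before randomisation: a participant who withdraws consent, or who "develops a violation of the selection criteria before randomization is defined as a screening failure", with no follow-up. It then adds a second group, participants who withdraw consent or "who do not fulfil inclusion/exclusion criteria after obtaining informed consent AND have not received any study medication will be withdrawn from the study". It says that withdrawn participants are not replaced and refers to 9.2.5 for follow-up.
- **8.5**: "Patients who are withdrawn from the study because they did not receive any study medication will not be followed up".
- **9.2.5** sets a general rule, "Patients who are withdrawn from the study will remain in the trial for the purpose of follow-up and data analysis", and then makes exceptions. One is: "Patients who are withdrawn because they have not received any study medication will not be followed up and will not receive a final study assessment".

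The analysis sections assume something else. In **11.4.1**, "The FAS/ITT Population is defined as all patients who are randomly allocated to a study arm", analysed as allocated, and this is the primary efficacy set. Sections 11.4.1 and 11.5 fill missing primary scores by LOCF. Section 8.1.1 says that the control group gets no study medication.

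On a neighbouring matter, 8.5 says "Patients who withdraw informed consent will not be followed up", whereas 9.2.5 has such patients asked for the week-4 assessment, which they may refuse.

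**The concern.** An ITT analysis of all randomised patients needs outcomes on all randomised patients. Here the protocol tells sites to stop collecting them for a group that the primary analysis still counts, and supplies a carried-forward score instead. For a patient withdrawn on day 0 or 1, that score is essentially the baseline value, a 3 or 4 under the stated hypothesis. Recovery, intubation or death by day 7 would go unseen, as would the day-14 endpoints, four-week mortality and adverse events.

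The condition that triggers this, having had no study medication, does not mean the same thing in both arms. It is always true of a control and true of a conestat patient only before the first dose. In an open-label trial, staff also know the arm when eligibility is re-judged. Losses that depend on the arm weaken the protection that section 6.2 expects from randomisation. No analysis plan can recover outcomes that were never collected.

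**Working it through.** **1. Does the rule reach randomised patients?** Section 7.4 handles violations arising before randomisation as screening failures. If its second rule covered only that stage it would be redundant, and its no-medication condition would be empty, because nobody receives study medication before randomisation. Nothing in 8.5 or 9.2.5 confines the exception to patients not yet randomised. As worded, the rule reaches them.

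**2. Is the trigger the same in the three sections?** No. Section 7.4 requires ineligibility plus no medication (or consent withdrawal). Sections 8.5 and 9.2.5 give non-receipt alone as the reason.

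**3. How does it act by arm?**

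| Reading | Control arm | Conestat arm |
|---|---|---|
| 7.4 as worded | An ineligible patient can always be withdrawn | An ineligible patient is withdrawn only before the first dose |
| Rule meant for the conestat arm only | Nobody is withdrawn under it | Undosed patients are withdrawn |

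Both readings are asymmetric, in opposite directions.

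**4. Size.** The point concerns no stated figure, and the documents give no rate of such patients, so what follows is illustration. The inputs from 11.2 are an effect of 1 point, SD 1.5, 80 + 40 patients, and Pocock level 0.0221 at three looks. They are coherent. A t-test at 80% power needs 36.3 per arm, and 36.3/0.955 (Wilcoxon efficiency) = 38.0, matching the plan's 2 × 38. Simulating three equally spaced looks at 0.0221 gives overall alpha 0.0498.

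*Controls only (7.4 as worded).* If k of 40 controls carry a score that is e points wrong, the control mean shifts by k × e/40.

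- True score 6, carried 4, k = 2: 2 × 2/40 = 0.10 too low, which shrinks the apparent benefit.
- True score 2, carried 4, k = 2: 0.10 too high, which flatters conestat alfa.
- At the first interim look, with 40/3 ≈ 13 controls, one such patient shifts the mean by 2/13 ≈ 0.15.

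*Undosed conestat patients only.* Let f be the undosed fraction. Assume that undosed patients have the control day-7 mean, and that their baseline lies g points above it.

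- Difference with full follow-up: (1 − f) × 1
- Difference with baseline carried forward: (1 − f) − f × g
- Power: drift d/(1.5 × √(1/80 + 1/40)) = d/0.290, tested at the Pocock level

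| f | Full follow-up: difference, power | Carried forward, g = 0.5 | g = 1.0 | g = 1.5 |
|---|---|---|---|---|
| 0 | 1.00, 89% | – | – | – |
| 5% (4 of 80) | 0.95, 86% | 0.925, 84% | 0.90, 82% | 0.875, 80% |
| 10% (8 of 80) | 0.90, 82% | 0.85, 77% | 0.80, 72% | 0.75, 66% |

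The shift caused by not following patients is f × g: from 0.05 × 0.5 = 0.025 to 0.10 × 1.5 = 0.15 points. If undosed patients worsen instead, the sign reverses. With g = −1 and f = 5%, the carried-forward difference is 0.95 + 0.05 = 1.00, against 0.95 with follow-up.

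These are mean-scale guides. The planned test is a stratified nonparametric one.

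**The case against.** The strongest case against is that the plan is not formally inconsistent. Section 11.4.1 keeps every randomised patient in the FAS/ITT set and says how missing scores are handled. That stands: a reader might infer that these patients are dropped from the ITT set, and no text drops them. The fault is avoidable missing data.

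Three other strong readings are tempting and not supported.

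- **Every control is to be withdrawn.** Taken literally, non-receipt in 8.5 describes the whole control arm, which cannot be intended. The documents leave open whether ineligible controls are meant.
- **Conestat patients who deteriorate or leave before the first dose are lost, so the loss is outcome-related.** Section 7.4 does not list non-receipt alone as a ground for withdrawal, and the default in 9.2.5 is continued follow-up. This is one reading of 8.5 and 9.2.5, and entry criteria are largely fixed before randomisation.
- **The result is biased by a predictable amount.** If 5% of each arm were affected with the same 2-point error, the shifts would be 2 × 2/40 = 0.10 and 4 × 2/80 = 0.10, and the difference would not move. Only unequal loss or unequal error matters, and neither is quantified.

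It is also fair that few patients should be affected. Section 9.3.1 lists the eligibility check immediately before randomisation, and treatment usually starts the same day. LOCF does not always mean baseline either, since scores are recorded daily and a later withdrawal carries a later score.

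What remains is that sites are told not to observe outcomes that the primary analysis needs, under a condition that differs by arm.

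**Conclusion.** The point holds as a defect in data collection. Sections 7.4, 8.5 and 9.2.5 allow randomised patients without study medication to go unfollowed, while 11.4.1 counts them in the primary analysis through LOCF. The loss is arm-dependent on either reading, and the three sections disagree on the trigger.

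Its size cannot be derived from the documents. Under the assumptions shown (5% to 10% of the conestat arm undosed, carried scores 0.5 to 1.5 points too high), the day-7 difference moves by 0.025 to 0.15 points beyond the dilution that full ITT follow-up would show. The direction depends on how the unobserved patients fare. The true number is probably small, so this is a reason to correct the wording and not evidence that the primary result would change.

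The mismatch between 8.5 and 9.2.5 on consent withdrawal is real but minor. It concerns the week-4 assessment and does not bear on the day-7 endpoint.

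**What to change.** Reconcile 7.4, 8.5 and 9.2.5 in one amendment.

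1. State that every randomised patient, dosed or not and whether or not later found ineligible, is followed for the WHO score to day 14 and for the week-4 assessment, unless consent to data collection is withdrawn.
2. Restrict withdrawal without follow-up to patients not yet randomised, that is, to the screening failures that 7.4 already defines.
3. Use one wording of the trigger in all three sections. Ineligibility found after randomisation can be dealt with through the per-protocol set, which already excludes major eligibility violations.
4. As a separate small correction, make 8.5 and 9.2.5 agree on whether patients who withdraw consent are asked for the week-4 assessment.

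The cost is amendment wording, a few extra scores read from charts and a few phone calls. Sample size and treatment rules are unaffected.
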